# 5 Statistical methods for Pharmacokinetic (PK) parameters

All subjects within the PK analysis set will be included in the PK data analysis.

### 5.1 Variables

Company Confidential Information

# 5.2 Descriptive analyses

# 6 Statistical methods for Efficacy /Pharmacodynamic (PD) parameters

Company Confidential Information

## 6.1 Primary objective

To determine whether treatment with CJM112 in patients with inadequately controlled moderate to severe asthma leads to an improvement in airflow obstruction.

#### 6.1.1 Variables

Company Confidential Information

### 6.1.2 Descriptive analyses

**Company Confidential Information** 

### 6.1.2.1 Graphical presentation of results

Company Confidential Information

#### 6.1.3 Statistical model, assumptions and hypotheses

# 6.2 Handling of missing values/censoring/discontinuations

The repeated measures analysis includes all available information in terms of measurements at all times. If missing measurements are assumed missing at random, an analysis of the available

data provides consistent estimates of model parameters, i.e. given observed data the missingness does not depend on unobserved data. Alternative assumptions may be explored to investigate the robustness of the results under plausible non-missing at random situations. Reasons for dropouts will be explored.

A Kaplan Meier plot of time to dropout (any reason) will be produced to assess dropouts.

#### Company Confidential Information

The inclusion of the data of subjects who miss at least one dose will be determined on a case-by-case basis, and will be decided during the Protocol Deviation assignment in a blinded fashion.

For spirometry assessments, a pre- and post-bronchodilator assessment should be conducted during baseline and at visits 105, 107, 201, and 299. Both short and long acting bronchodilators must be withheld prior to the study visits as described in the SOM, patients must be instructed to withhold bronchodilators (both short and long acting) prior to performing spirometry at applicable visits, as follows:

- Short-acting  $\beta$ 2-agonists (SABAs)  $\geq$  6 h
- SAMA  $\geq 8 \text{ h}$
- Long-acting bronchodilators (LABAs and LAMAs) given twice daily  $\geq 24 \text{ h}$
- Long-acting bronchodilators (LABAs and LAMAs) given once daily  $\geq 48 \text{ h}$

When bronchodilators are given combined with ICS, the ICS component will have to be withheld as well. When such situation arises, and rescheduling of the visit is not possible, the spirometry test results and other parameters that involves Spirometry results, e.g. ACQ7, will be omitted from analysis for that visit.

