4.1 Inclusion criteria

Population eligible for inclusion in this study must fulfill all of the following criteria:

- 1. Written informed consent must be obtained before any assessment is performed
- 2. Able to communicate well with the investigator, to understand and comply with the requirements of the study.
- 3. Male and female adult patients aged ≥ 18 to ≤ 75 years.
- 4. Patients must weigh between 50 and 120 kg

- Amended Protocol Version v02 (Clean)
- 5. Patients with a physician-diagnosed history of moderate to severe asthma for a period of at least one year prior to screening
- 6. Patients on a stable therapy regimen for asthma for at least 3 months prior to screening with at least medium dose inhaled glucocorticoid and at least one additional asthma control medication (such as inhaled long-acting bronchodilator, leukotriene antagonist, theophylline, stable low dose glucocorticoid, etc)
- 7. Acceptable and reproducible spirometry with FEV1 > 40 and < 90 % of predicted at screening and baseline visits (Re-testing is allowed once)
- 8. ACQ score ≥ 1.5 at screening and baseline visits (Re-testing is allowed once)
- 9. Total serum IgE < 150 IU/mL at screening and baseline visits (Re-testing is allowed once)
- 10. Peripheral blood eosinophils < 300/μL at screening and baseline visits (Re-testing is allowed once)

4.2 **Exclusion criteria**

Population fulfilling any of the following criteria are not eligible for inclusion in this study:

- 1. Use of investigational drugs at the time of screening, or within 4 weeks or 5 half-lives of screening, or as required by local regulations, whichever is longer.
- 2. Treatment with IL-17 or IL-17R blocking agents over the previous 12 months, including, but not limited to secukinumab, ixekizumab, bimekizumab and brodalumab.
- 3. Previous use of biologics or other concomitant medications within time periods specified in the SOM/protocol.
- 4. Women of child-bearing potential, defined as all women physiologically capable of becoming pregnant, unless they are using highly effective methods of contraception during dosing and for 13 weeks after stopping of investigational drug. Highly effective contraception methods include:
 - Total abstinence from heterosexual intercourse (when this is in line with the preferred and usual lifestyle of the subject). Periodic abstinence (e.g. calendar, ovulation, symptothermal, post-ovulation methods) and withdrawal are not acceptable methods of contraception.

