6.10 Rescue medication

Use of short-acting rescue inhalers/bronchodilators for asthma, such as albuterol/salbutamol, is permitted. They must be sourced by the investigational site or the subjects themselves. Both short and long acting bronchodilators must be withheld prior to the study visits as described in the SOM. No other specific rescue treatments are planned for this study. Use of rescue medication must be recorded on the Concomitant medications/Significant non-drug therapies CRF.

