# 2 First interpretable results (FIR)

# 3 Interim analyses

## 4 Statistical methods: Analysis sets

For subjects for which the actual treatment received does not match the randomized treatment the treatment actually received will be used for the analysis.

The safety analysis set will include all subjects that received any study drug.

The PK analysis set will include all subjects with at least one available valid (i.e. not flagged for exclusion) PK concentration measurement, who received any study drug and experienced no protocol deviations with relevant impact on PK data.

The PD analysis set will include all subjects with any available PD data and experienced no protocol deviations with relevant impact on PD or efficacy data. If a subject has an asthma exacerbation adverse event during the study, all subsequent efficacy assessments will be excluded from the PD analysis set.

The analysis sets and protocol deviation codes are related as follows:

Table 4-1 Protocol deviation codes and analysis sets

Category Deviation code	Text description of deviation	Data exclusion	
Subjects are exclude	ded from PD analysis in case of these PDs:	Exclude subject from PD analysis set	
INCL05	Deviation from inclusion criterion 5	Yes	
INCL07	Deviation from inclusion criterion 7	Yes	
EXCL01	Deviation from exclusion criterion 1	Yes	

Page 16

CJM112X2204

Category Deviation code	Text description of deviation	Data exclusion
EXCL02	Deviation from exclusion criterion 2	Yes
EXCL03	Deviation from exclusion criterion 3	Yes
EXCL07	Deviation from exclusion criterion 7	Yes
EXCL20	Deviation from exclusion criterion 20	Yes
EXCL21	Deviation from exclusion criterion 21	Yes
EXCL22	Deviation from exclusion criterion 22	Yes
COMD01	Use of prohibited medication during the study	Yes ( from this visit onwards)
WITHO1	Patient who met withdrawal criteria but were not withdrawn	Yes (from the visit subjects met withdrawal criteria onwards)

If updates to this table are needed, an amendment to the SAP will be implemented prior to DBL.

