# 10 Appendix 1: Historical clinical trials use in meta-analyses of informative prior of FEV1.

Table 10-1 Mean change from baseline of FEV1 (L) at Week 12 in the placebo group of the selected six studies

Selected study	Selected population	n	FEV1 change from baseline (L)	SE
AIN457D2204	IgE < 100 IU/ml	7	0.007	0.098
QBX258X2201	IgE <400 IU/ml	9	0.015	0.116
QAW029A2206	overall	136	0.038	0.039
QAW039A2214	non-atopic	93	0.03	0.029
Dupilumab				
(Wenzel et al, 2016)	eos count < 300	71	0.1	0.040
Brodalumab				
(Busse et al, 2013)	overall	76	0.056	0.036

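### Does SAP 6.2 leave open which visits lose their spirometry and ACQ7 results?

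*SAP*

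**What the plan says.** The passage is in SAP 6.2, on missing values and discontinuations. It first says that "a pre- and post-bronchodilator assessment should be conducted during baseline and at visits 105, 107, 201, and 299". It then gives minimum withholding times in hours, by class of bronchodilator, and adds: "When bronchodilators are given combined with ICS, the ICS component will have to be withheld as well". The omission rule comes next. It opens "When such situation arises, and rescheduling of the visit is not possible, the spirometry test results and other parameters that involves Spirometry results" and, after naming the asthma control score as an example, closes "ACQ7, will be omitted from analysis for that visit".

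Other relevant text:

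- SAP Table 4-1 links deviation codes to data exclusion. The nearest code is COMD01, "Use of prohibited medication during the study". No code is specific to a missed withholding time.
- Protocol Table 5-1 lists no bronchodilator among the prohibited drugs, and Protocol 6.10 says: "Use of short-acting rescue inhalers/bronchodilators for asthma, such as albuterol/salbutamol, is permitted". It also requires bronchodilators to be withheld before visits and leaves the detail to the Site Operations Manual.
- Protocol 4.1, criterion 6, requires "at least medium dose inhaled glucocorticoid and at least one additional asthma control medication", with a long-acting bronchodilator as the first example.
- Protocol 3.7 says that participation should be reconsidered for a patient who cannot withhold, but states no consequence for the data.

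**The concern.** The omission rule points back to a situation that no earlier sentence describes as a failure. The sentence just before it describes a patient who withholds a combination inhaler, steroid included, as instructed. Read strictly, the rule would remove FEV1 from visits done correctly and would give no ground for removing FEV1 measured under bronchodilator effect.

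FEV1 change from baseline is the primary endpoint. FEV1 % predicted and any ACQ7-based result would be affected as well. Every patient takes an inhaled steroid plus another controller, so users of combination inhalers could be numerous, although their share is not given. Table 4-1 offers no fallback, because rescue bronchodilators are permitted and so fall outside COMD01. Two programmers working only from this sentence could select different visits.

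**Working it through.** **Step 1. Test both readings against the sentence.** The rule has two conditions: the situation arises, and the visit cannot be rescheduled.

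| | Reading A: combination product correctly withheld | Reading B: withholding times not met |
|---|---|---|
| Reason to reschedule? | None; the test is valid | Yes; the patient can withhold before a new date |
| Would a new date cure it? | No; the patient still uses the same inhaler | Yes |
| Fit with the instruction just before | Contradicts it: patients withhold, and the result is then discarded | Gives the consequence of not following it |

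Reading A leaves the rescheduling condition without a purpose. Only B gives every clause work to do.

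**Step 2. Is Table 4-1 the place for this rule?** Its entries exclude a subject, or data from a given visit onwards. A missed washout spoils one visit. A visit-level rule in SAP 6.2 is the natural home, so the lack of a code is not a gap.

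**Step 3. Are post-bronchodilator values covered?** The paragraph names both assessments as part of the visit's spirometry and then omits the spirometry results for that visit without qualification. Both are covered.

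**Step 4. What is the scale?** The sample-size section (Protocol 11.7) and the primary model (SAP 6.1.3) are not visible, so the plan has no figure to reproduce. For illustration only:

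- Inputs: SE and n from SAP Table 10-1, "Mean change from baseline of FEV1 (L) at Week 12 in the placebo group of the selected six studies"; about 110 patients randomized 3:2, which is 66 and 44.
- SD = SE × √n, taking each SE as that of a raw mean: 0.098 × √7 = 0.259; 0.116 × √9 = 0.348; 0.039 × √136 = 0.455; 0.029 × √93 = 0.280; 0.040 × √71 = 0.337; 0.036 × √76 = 0.314 L. Pooled by degrees of freedom: 0.366 L.
- SE of the difference at one visit = 0.366 × √(1/66 + 1/44) = 0.366 × 0.1946 = 0.071 L, or 71 mL. Over the range of SDs it is 51 to 89 mL.
- With a share q omitted equally in both arms, the SE is divided by √(1 − q):

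| q (assumed) | SE, mL | Increase |
|---|---|---|
| 0 | 71.3 | – |
| 5% | 73.2 | 2.6% |
| 10% | 75.2 | 5.4% |
| 20% | 79.7 | 11.8% |
| 50% | 100.9 | 41.4% |

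The 50% row could arise only under Reading A, with half the patients on combination inhalers and also unable to reschedule. Nothing in the documents supports it.

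**The case for a change.** The best case for a change is that an exclusion from the primary endpoint should not rest on inference. No visible text states the trigger, and the fix is short. SAP 6.2 says that missed doses are judged under blind but names no decider for spirometry. SAP 1.4 plans at least two interim analyses, and Protocol Table 6-2 allows statisticians and programmers to be unblinded then. A trigger settled late could be settled by people who know the allocation. Omissions after recent rescue use may also reflect current airflow, which strains the missing-at-random assumption.

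Part of this stands. The sentence is badly drafted, and stating its trigger would be a courtesy to the reader. The rest has little weight. The withholding times are fixed numbers of hours by drug class, so once the intent is read correctly there is little left to choose. SAP 1.1 places derivation detail in a separate programming specification, and Protocol 8.5 sends lung function reports to central reading, so programmers would not be working from this sentence alone. SAP 6.2 already allows other missing-data assumptions to be explored, and a clearer trigger would not alter why those visits are lost.

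One could also ask for an ACQ score without the FEV1 item at affected visits. That keeps some data but mixes visits scored on different items. It is a trade-off rather than a correction, and SAP 6.3.1 and 6.3.3, where such a score might be defined, are redacted. A table of omitted visits by arm would be informative but would change no result.

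A bias of 5 to 20 mL can be obtained by multiplying an assumed 5 to 10 point arm difference in failed washout by an assumed bronchodilator effect of 100 to 200 mL. It arises only if the affected values are kept, and the rule removes them.

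**Conclusion.** The wording is loose but the rule is sound. Read as a whole, the sentence omits spirometry and spirometry-based scores from a visit where the withholding times were missed and a new date was not possible. It retains visits where a combination inhaler was properly withheld. Analysts would reach that reading without help, so this is a clerical slip and the plan need not change.

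On that reading the cost is the loss of the affected visits. At assumed losses of 5% to 10%, equal in both arms, the single-visit standard error rises by about 3% to 5%. This uses an SD back-calculated from Table 10-1 and a simple two-group comparison; the actual model is not visible. The true rate of missed withholding is unknown.

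The conclusion rests on the rescheduling clause and the subject of the paragraph. It would be weaker only if the Site Operations Manual or the redacted text tied the rule to correctly withheld combination products, and nothing visible suggests that.

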# 6.3 Secondary objectives

[figure not shown]
To determine whether treatment with CJM112 in patients with inadequately controlled moderate to severe asthma leads to an improvement in

- FEV1% of predicted.
- asthma control

### 6.3.1 Variables

Company Confidential Information

## 6.3.2 Descriptive analyses

Page 21 CJM112X2204

## 6.3.3 Statistical model, hypothesis, and method of analysis

Company Confidential Information

# 6.4 Exploratory objectives

## 6.4.2 Descriptive analyses

Company Confidential Information

# 6.4.3 Statistical model, assumptions and hypotheses

# 7 Statistical methods for safety and tolerability data

All subjects within the safety analysis set will be included in the safety data analysis.

## 7.1 Variables

Adverse events, vital signs (blood pressure, pulse rate, body temperature, oxygen saturation by pulse oximetry), ECG intervals, laboratory measurements, as well as subject demographics, baseline characteristics, and treatment information.

## 7.2 Descriptive analyses

#### Subject demographics and other baseline characteristics

All data for background and demographic variables will be listed by treatment group and patient. Summary statistics will be provided by treatment group.

Relevant medical history, current medical conditions, results of laboratory screens, drug tests and any other relevant information will be listed by treatment group and patient.

#### **Treatment**

Data for study drug administration, rescue medication and concomitant therapies will be listed by treatment group and patient.

### Vital signs

All vital signs data will be listed by treatment group, patient, and visit/time and if ranges are available abnormalities (and relevant orthostatic changes) will be flagged. Summary statistics will be provided by treatment group and visit/time.

#### **ECG** evaluations

All ECG data will be listed by treatment group, patient and visit/time, abnormalities will be flagged. Summary statistics will be provided by treatment group and visit/time.

## Clinical laboratory evaluations

All laboratory data will be listed by treatment group, patient, and visit/time and if normal ranges are available abnormalities will be flagged. A separate listing is provided presenting all parameters in a subject with any abnormal values. Summary statistics will be provided by treatment group and visit/time.

Boxplots of laboratory data will also be provided.

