Title	A randomized, subject- and investigator-blinded, placebo-controlled, multi-center, multiple dose study to assess the efficacy and safety of CJM112 in patients with inadequately controlled moderate to severe asthma		
Brief title	Study of safety and efficacy of CJM112 in moderate to severe asthmatics		
Sponsor and Clinical Trial Phase	Novartis Phase II		
Intervention type	Biologic		
Study type	Interventional		
An unmet medical need exists for patients with moderate and severe as who continue to demonstrate symptoms despite being on standard of medications, and are not eligible for other biologic therapies developed development for T2-high (allergic/eosinophilic) asthma (such as omaliz and mepolizumab) because they have low circulating IgE and eosinophil at baseline. The purpose of this study is to determine if CJM112, an anti-Il antibody, when added to existing therapy, displays the clinical efficacy safety profile to support further development in patients with inadequence controlled moderate to severe asthma with low IgE and low circulating IgE and low circulating IgE and I			
Primary Objective(s)	To determine whether treatment with CJM112 in patients with inadequately controlled moderate to severe asthma leads to an improvement in airflow obstruction as reflected by change from baseline in FEV1 in mL.		
Secondary Objectives	To determine whether treatment with CJM112 in patients with inadequately controlled moderate to severe asthma: 1. leads to an improvement in FEV1% of predicted. 2. leads to an improvement in asthma control as reflected by change from baseline in ACQ score 3. is safe and well tolerated by evaluating study treatment discontinuations and adverse events		
Study design	12 week, non-confirmatory, randomized, subject- and investigator-blinded, placebo-controlled, multi-center, parallel-arm study in which patients will be randomized 3:2 to CJM112:placebo.		
Population	The study population will consist of approximately 110 male and female patients between 18 and 75 years old with uncontrolled symptoms of moderate or severe asthma (defined by ACQ score of ≥1.5) who are compliant on standard of care medications.		

	1. Patients with a physician-diagnosed history of moderate to severe asthma for a period of at least one year prior to screening.		

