3.1 Study design

This is a non-confirmatory, randomized, subject- and investigator-blinded, placebo-controlled, multi-center, parallel-arm study evaluating the efficacy of CJM112 on top of standard of care in patients with inadequately controlled moderate to severe asthma. This study will enroll approximately 110 patients. After an initial screening visit and run-in period of approximately 4 weeks, subjects eligible per inclusion and exclusion criteria at the baseline visit will be randomized (3:2) to receive Company Confidential Information CJM112 or matching placebo subcutaneously over 3 months during visits at the clinical study site. All baseline safety evaluation results must be available prior to the first dose. After the end of the treatment period, subjects will be followed for an additional 13 weeks. Site visits to administer dose and assess safety and efficacy will be scheduled as depicted in the figure below.

Figure 3-1 Study Design

Company Confidential Information

Screening and Run-In: Patients will provide informed consent and participate in an initial screening visit consisting of vital signs, physical exam, blood chemistry, ECG, pulmonary function tests, and ACQ. Subjects who meet all eligibility criteria at the screening visit will be dispensed a daily symptom diary and be asked to perform peak flow measurements over the approximately 4 week run-in period until the baseline visit.

Baseline: Subjects who qualify based on screening and run-in assessments will return for a baseline evaluation between Day -5 to Day -2. Subjects who meet all the applicable inclusion/exclusion criteria at screening and baseline will be randomized and will enter the treatment period. All screening and baseline assessments results must be available prior to randomization.

Treatment Period:

Company Confidential Information

At treatment period visits, safety, Company Confidential Information assessments will be performed. Safety assessments will include physical examinations, open ended health inquiry, ECGs, vital signs, standard clinical laboratory evaluations (hematology, blood chemistry, urinalysis), AEs and SAE monitoring.

Company Confidential Information

Company

Safety Follow-up: After completing the last dose Confidential Information, subjects will enter an additional follow-up period consisting of a visit on Day 92, Day 134 and an End of Study (EOS) visit on Day 176.

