Hypersensitivity reactions have not been observed so far for CJM112, but their future occurrence cannot be excluded. Study subjects should be monitored post-injection for hypersensitivity and anaphylaxis events for an appropriate amount of time, no less than 30 minutes post-dose. Injection site reactions, elevations in liver enzymes, drops in neutrophil counts and ECG abnormalities have been observed sporadically and very rarely in secukinumab trials. These constitute events that may be observed and should be monitored routinely, as with any investigational biologic treatment.

Company Confidential Information

Due to the early stage of development, there may be unknown risks of CJM112 which may be serious and/or unforeseen.

Amended Protocol Version v02 (Clean)

Additional risks to study subjects are related to the procedures of this clinical trial, such as withholding bronchodilators prior to lung function tests and blood sampling. During the collection of blood samples, patients may experience pain and/or bruising at the injection site. In addition, although rare, localized clot formation, infections and nerve injuries may occur. Lightheadedness or fainting may also occur during or after the blood draw.

Certain adverse events, such as shortness of breath, wheezing, cough, chest tightness and asthma flares or exacerbations may occur in study participants. These risks are inherent to the disease process and are unlikely to be caused or worsened by CJM112 or study participation. except when bronchodilators are withheld prior to lung function tests. If a subject is unable to withhold bronchodilators prior to lung function tests, he/she should be treated appropriately and his/her participation in this study should be re-considered.

3.7.1 **Blood sample volumes**

Approximately 400 mL of blood is planned to be collected over a period of 16 weeks, from each subject as part of the study. Additional samples collected for monitoring of any safety findings would be in addition to this pre-specified volume. This is not considered to be a risk for this population.

Timings of blood sample collection are outlined in the Assessment schedule, Section 8.1.

A summary blood log is provided in the Site Operations Manual, together with instructions for all sample collection, processing, storage, and shipment information.

See Section 8.9 regarding the potential use of residual samples.

4 **Population**

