7.2 Discontinuation of study treatment

Discontinuation of study treatment for a subject occurs when study treatment is stopped earlier than the protocol planned duration. Discontinuation of study treatment can be decided by either the subject or the investigator.

Study treatment must be discontinued under the following circumstances:

- Subject decision subjects may choose to discontinue study treatment for any reason at any time.
- The investigator believes that continuation would negatively impact the safety of the subject or the risk/benefit ratio of trial participation.
- Any protocol deviation that results in a significant risk to the subject's safety.
- Pregnancy (see Section 8.6 (Safety) and Section 9.6 (Pregnancy reporting))
- Adverse events, abnormal laboratory values or abnormal test result that indicate a safety risk to the subject.
- Patients who experience an asthma exacerbation during the treatment epoch that requires treatment with systemic corticosteroids.
- Patients with > 50% decrease in FEV₁ confirmed by a repeat measurement during the study period.
- Emergence of the following severe adverse events:
 - Severe, grade 3 or higher allergic or hypersensitivity reaction
 - Severe, acute, grade 3 or higher infection as judged by the investigator
 - Severe neutropenia grade 3 or higher
- If a liver or renal event occurs, follow guidelines outlined in Appendix 1 and Appendix 2 regarding discontinuation of study treatment.
- Any laboratory abnormalities that in the judgment of the investigator, taking into consideration the subject's overall status, prevents the subject from continuing participation in the study.

Treatment for patients experiencing an asthma exacerbation with systemic steroids is considered standard of care. The dose and duration for such treatment will be left at the discretion of the clinical site study investigator, so that appropriate treatment can be tailored to the severity of the patient's clinical condition. Treatment discontinuations due to asthma exacerbations will be considered "treatment failures".

Use of prohibited treatment as per Table 5-1 might result in treatment discontinuation (decision will be taken on case by case basis after consultation with Sponsor).

The appropriate personnel from the site and Novartis will assess whether investigational drug treatment should be discontinued for any subject whose treatment code has been broken inadvertently for any reason.

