9.3 Liver safety monitoring

To ensure subject safety and enhance reliability in determining the hepatotoxic potential of an investigational drug, a standardized process for identification, monitoring and evaluation of liver events has to be followed.

Please refer to Table 15-1 in Appendix 1 for complete definitions of liver events.

Follow-up of liver events

Every liver event defined in Table 15-1 of Appendix 1 should be followed up by the investigator or designated personnel at the trial site, as summarized below. Additional details on actions required in case of liver events are outlined in Table 15-2 of Appendix 1.

- Repeating liver chemistry tests (ALT, AST, TBL, PT/INR, ALP and γGT) to confirm elevation within 48-72 hours.
 - These liver chemistry repeats should always be performed using the central laboratory, with the results provided via the standard electronic transfer. If results will not be available from the central laboratory within 24 hours, then the repeats can also be performed at a local laboratory to monitor the safety of the subject. If a liver event is subsequently reported, any local liver chemistry tests previously conducted that are associated with this event should have results reported on the unscheduled local laboratory CRF.
 - If the initial elevation is confirmed, close observation of the subject will be initiated, including consideration of treatment interruption if deemed appropriate.
- Discontinuation of the investigational drug (refer to Section 7.2 (Discontinuation of study treatment), if appropriate
- Hospitalization of the subject if appropriate
- Causality assessment of the liver event
- Thorough follow-up of the liver event should include:
 - Repeating liver chemistry tests two or three times weekly. Testing should include ALT, AST, ALP, PT/INR, and gGT. If total bilirubin is elevated > 2 x ULN, fractionation into direct and indirect bilirubin is required. To rule out muscular origin of transaminase elevations, CPK should be measured along with liver chemistry tests. Frequency of retesting can decrease to once a week or less if abnormalities stabilize or the study drug has been discontinued and the subject is asymptomatic. Retesting should be continued up to resolution.
 - Obtaining a more detailed history of symptoms and prior or concurrent diseases.

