#### Other safety evaluations

#### **Immunogenicity**

All immunogenicity results will be listed by subject and visit/time.

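### SAP 7.2 plans no per-arm count of patients whose laboratory or ECG values cross the protocol's own limits; asymptomatic ALT/AST rises are the main gap

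*SAP*

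**What the plan says.** Protocol 3.7 sets out the expected risks: "Injection site reactions, elevations in liver enzymes, drops in neutrophil counts and ECG abnormalities have been observed sporadically and very rarely in secukinumab trials". It adds that they may be seen in this study and should be monitored routinely. The protocol gives limits for three of the four:

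- **Liver:** Table 15-1 has isolated ALT/AST tiers above 3, 5 and 8 x ULN, and a potential Hy's law combination.
- **Neutrophils:** Section 7.2 lists "Severe neutropenia grade 3 or higher" among the severe adverse events that require study treatment to stop.
- **ECG:** Section 8.6.2 gives QTcF above 500 ms as an example of a clinically significant abnormality. It requires clinically significant abnormalities to be entered on the AE form.

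For the analysis, SAP 7.2 says under both the laboratory and the ECG headings: "Summary statistics will be provided by treatment group and visit/time". Both kinds of data are also listed with abnormalities flagged. Laboratory data get a further listing for patients with any abnormal value, and boxplots. AEs are tabulated as number and percentage per arm by preferred term, by maximum severity and by relationship to study drug. The safety set is everyone who received study drug.

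**The concern.** Harms that appear sporadically are a matter of how many patients were affected. A summary by visit answers a different question, namely where the group's values lay at that visit. Safety and tolerability is a secondary objective, and the study is meant to show whether the safety profile supports further development. A reader of the report would want the number of patients per arm who passed 3, 5 or 8 x ULN, and the readable plan does not produce it. An analyst could count from the listings after unblinding, but the choice of limits, and whether unscheduled values count, would then be made with the results in view.

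**Working it through.** The plan states no figure on this point, so there is none to reproduce. The check sets the recording rules beside the analysis rules, then uses simple arithmetic to show the scale.

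**1. What reaches a per-arm count.** Under Protocol 9.1 an abnormal result becomes an AE only if it causes signs or symptoms, is considered clinically significant, or needs therapy.

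| Limit in the protocol | Route to an AE | Counted per arm? |
|---|---|---|
| Neutropenia, grade 3 or higher (7.2) | Listed there as a severe adverse event | Yes, as an AE term |
| QTcF > 500 ms (8.6.2) | Example of a clinically significant finding, for the AE form | Yes, as an AE term |
| ALT/AST elevation with symptoms (Table 15-1) | Meets the symptom criterion | Yes, as an AE term |
| Isolated ALT/AST > 3 to 5 x ULN, no symptoms (Table 15-2) | Only if judged clinically significant or treated; the action shown is monitoring | Not necessarily |
| Isolated ALT/AST in higher tiers, no symptoms | Same criteria, though a judgement of significance is more likely | Depends on that judgement |

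**2. What the AE tables can show.** Severity in Protocol 9.1 is mild, moderate or severe, according to interference with normal activities. A marked laboratory change without symptoms could be recorded as mild. A preferred term carries no multiple of ULN. So even recorded AEs cannot be sorted by threshold.

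**3. What the by-visit summaries can show.** Protocol 9.3 asks for a liver repeat within 48-72 hours, then testing two or three times weekly. Repeats are to go to the central laboratory, with a local laboratory also allowed if central results would be late. For those, "any local liver chemistry tests previously conducted that are associated with this event should have results reported on the unscheduled local laboratory CRF". Peak values therefore have no common scheduled visit. A patient who stops treatment moves to visit 201 about 7 days after the last treatment visit, then to 202 and 299 (Protocol 7.1), and so contributes nothing to the remaining treatment-visit summaries.

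**4. Dilution in a mean.** Inputs from the documents: "This study will enroll approximately 110 patients" (Protocol 3.1) and "patients will be randomized 3:2 to CJM112:placebo" (Protocol synopsis). Hence 110 x 3/5 = 66 and 110 x 2/5 = 44. All means, SDs, extreme values and event counts below are assumptions.

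Shift in the arm mean = k x (distance of the extreme from the typical value) / 66. Standard error (SE) of the arm difference = SD x sqrt(1/66 + 1/44).

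- ALT, typical 0.6 x ULN, SD 0.3: SE = 0.058. One patient at 3 x ULN gives 2.4/66 = 0.036, or 0.6 SE. Three patients at 5 x ULN at the same visit give 3 x 4.4/66 = 0.20, or 3.4 SE.
- Neutrophils, mean 4.5, SD 1.5 (x10^9/L): SE = 0.29. Three patients at 0.9 give 3 x 3.6/66 = 0.16, or 0.56 SE.
- QTcF, mean 410, SD 20 (ms): SE = 3.9. Three patients at 505 give 3 x 95/66 = 4.3, or 1.1 SE.

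A mean can hide a few extremes, but not always: several large ALT rises at one visit would show. The visible SAP plans no test of these means, so the SE is only a yardstick.

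**5. What a count would show.** Exact (Clopper-Pearson) 95% intervals:

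| Patients over a limit | Percentage | 95% CI |
|---|---|---|
| 0/66 | 0 | 0 to 5.4 |
| 1/66 | 1.5 | 0.04 to 8.2 |
| 3/66 | 4.5 | 0.9 to 12.7 |
| 0/44 | 0 | 0 to 8.0 |

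Fisher's exact two-sided p for 3/66 against 0/44 is 0.27, so the table describes and does not test.

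**The case against.** The strongest reply is that the AE tables already do most of this work. They give incidence per arm in all treated patients, and the two most serious limits outside the liver are routed to them. That stands. A reader might infer that the incidence of these harms is never estimated; the documents do not support that.

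A reader might also infer that patients who stop because of a harm are lost. They are not. They stay in the AE denominator, treatment discontinuation is itself a secondary endpoint with its reason recorded, and they are asked to attend visits 201, 202 and 299. Protocol 7.2 names only medications and AEs as the minimum data after stopping. The assessment schedule cannot be read, however, so nobody can say that laboratory tests or ECGs are missing at those visits. Only the remaining treatment-visit summaries lose these patients.

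Further limits also stand:

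- The flagged listings display individual extremes, although they do not count them by arm.
- The SAP does not say which statistics the summaries contain, so minimum and maximum may be included. It gives no visible rule on unscheduled values.
- Table shells and derivations sit in separate documents, and SAP 7.3 on graphs is withheld.
- The risk statement concerns secukinumab trials and says very rarely. It does not report these events for CJM112.
- The study is non-confirmatory, and the proposed table would not make the comparison conclusive.

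What the reply does not remove is the symptom-free ALT/AST rise that nobody records as an AE, and the loss of the threshold for those that are recorded.

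**Conclusion.** The point holds as a minor reporting gap. In the readable SAP 7.2, measured laboratory and ECG values are summarised between arms only by visit, and threshold crossings are counted per arm only through AE reporting. The gap is mainly asymptomatic ALT/AST elevation not judged clinically significant. For neutropenia and QTcF, a table based on measured values would chiefly cross-check the AE count. The size cannot be given as a bias or a loss of power, because the documents give no event rates and plan no test of these measures. It amounts to a missing descriptive proportion, whose precision with 66 and 44 patients is shown by the intervals above. The conclusion assumes that the withheld graphs section and the separate table shells do not already contain such a count.

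**What to change.** Keep the by-visit summaries and add one table to SAP 7.2. On the safety set, by treatment group, give the number and percentage of patients, with exact 95% confidence intervals, by worst value after first dose. Include scheduled, unscheduled and local-laboratory results, with liver values expressed relative to the reporting laboratory's own ULN. Use only limits already in the protocol:

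- ALT or AST above 3, 5 and 8 x ULN;
- the Table 15-1 potential Hy's law combination: ALT or AST above 3 x ULN with TBL above 2 x ULN and no initial ALP rise above 2 x ULN;
- neutropenia at the grade 3 level, with the grading scale named, since the readable protocol names none;
- QTcF above 500 ms.

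Label the table descriptive. It changes no clinical rule and needs no new visit or sample. The cost is a few lines of SAP text, one table, and the programming to normalise local and central values.
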